6.5 Efficacy

There are no efficacy assessments in the study.

6.6 Safety

Analysis of all safety data will follow the BMS guideline of analysis of safety data. The evaluation of safety is based on clinical AEs, vital signs, ECG results, and clinical laboratory results reported during the study.

All data collected from the sampling outside the scheduled visits will only be included in the listing and will be excluded from the summary tables.

6.6.1 Deaths

All reported deaths after a participant is enrolled (ie, has signed the informed consent) will be listed by participant.

6.6.2 Serious Adverse Events

All reported serious adverse events (SAEs) will be listed for all enrolled participants.

6.6.3 Adverse Events

Adverse events that occur on or after the administration of study treatment will be tabulated. Events occurring after discharge will be assigned to the study treatment received for up to 56 days after the termination of study drug. The proportion of participants having an AE will be calculated as the number of participants having the event in the specific treatment interval, divided by the total number of participants receiving study treatment during that treatment interval.

All AE listings will indicate the unique subject identifier, age, gender, current treatment, the date of onset, the date of resolution, day of onset relative to the start of treatment, action taken, investigator's assessment of severity, and relationship to study drug. The AE listing of all AEs will also include those AEs that occurred beyond 56 days after the termination of study drug. Additional listings will be provided for AEs leading to discontinuation and AEs without recorded resolution.

All AEs will be summarized by system organ class, preferred term, treatment and overall for all treated participants. Summaries of AEs will include AEs, AEs by intensity and AEs related to study drug.

Additional summaries will be provided for acute peri-infusional and postinfusional AEs that occurred during the 30-minute infusion period and the 24-hour post-infusion period, respectively, after the start of the abatacept infusion.

AE Counting Rules:

Where a participant has the same AE, based on preferred terminology, reported multiple times in a single analysis period, the subject will only be counted once at the preferred terminology level in AE frequency tables.

Where a participant has multiple AEs within the same system organ class in a single analysis period, the participant will only be counted once at the system organ class level in AE frequency tables.

When a participant has the same AE, based on preferred terminology, reported multiple times in a single analysis period, the following criteria, in order of precedence, will be used to select the event to be included in summary tables:

- Relationship to study medication
- Intensity of event
- Onset date and time

When reporting AEs by intensity, in addition to providing a summary table based on the event selection criteria detailed above, summary tables will also be provided based on the most intense event during the analysis period - independent of relationship to study medication. For these tables, the following criteria, in order of precedence, will be used to select the event to be included in summary tables:

- Intensity of event
- Onset date and time

Participants will only be counted once in the 'Total' at their maximum intensity, regardless of SOC or PT.

6.6.4 Injection Site Reaction

Injection site reaction data will be listed per participant and time point.

6.6.5 Clinical Laboratory Evaluations

The results of all protocol-specified clinical laboratory tests and corresponding change from baseline values will be listed by subject for all treated participants. Laboratory measurements and corresponding change from baseline values will be summarized by treatment and scheduled nominal visit for each laboratory test.

The criteria used for classifying laboratory test results as markedly abnormal will be listed.

Laboratory results will be classified as markedly abnormal based on sponsor defined criteria.

Laboratory results for participants with any marked laboratory abnormality (scheduled and unscheduled) will be listed. This listing will include all observations for the specific laboratory test and participant, not only the marked laboratory abnormality measurements. The frequency of participants with any marked laboratory abnormality, based on pre-specified criteria, will be presented.

6.6.6 **Electrocardiograms**

All recorded electrocardiograms (ECGs) will be listed for all treated participants.

QTcF will be made available in the database. If QTcF is not available in the database, QTcF will be calculated using the reported uncorrected QT interval and heart rate (HR), and the following formula:

$$QTcF = \frac{QT}{(60/HEART\ RATE)^{1/3}}$$

If QTcB is not available in the database, QTcB will not be calculated.

Summaries of ECG parameters (HR, QT (QT, QTcB, QTcF), PR, and QRS intervals) will be tabulated by study day and treatment. Summaries of ECG parameters will include change from baseline at Day 1, 3 hours after the start of infusion, and Day 71 (at discharge). Baseline will be considered as Day 1 pre-dose measurement.

Participants with ECG intervals outside of a pre-specified range and investigator identified ECG abnormalities will also be listed.

The following criteria will be used to determine ECG results that are outside of a pre-specified range:

PR (msec):	Value > 200
QRS (msec):	Value > 120
QT (msec):	Value > 500 or change from baseline > 30
QTcB (msec):	Value > 450 or change from baseline > 30
QTcF (msec):	Value > 450 or change from baseline > 30

6.6.7 **Vital Signs**

Vital signs parameters (systolic blood pressure, diastolic blood pressure, heart rate, respiratory rate, and body temperature) will be listed. Summaries of vital sign parameters will be provided for each vital sign parameter at corresponding visits by treatment and respective changes from baseline.

Participants with vital signs outside of a pre-specified range will also be listed.

The following criteria will be used to determine vital sign results that are outside of a pre-specified range, where changes from baseline are calculated as parameter value - baseline parameter value:

Heart Rate (bpm)	Value > 100 and change from baseline > 30, or Value < 55 and change from baseline < -15
Systolic BP (mmHg)	Value > 140 and change from baseline > 20, or Value < 90 and change from baseline < -20
Diastolic BP (mmHg)	Value > 90 and change from baseline > 10, or Value < 55 and change from baseline < -10
Respiration (breaths/min)	Value > 16 or change from baseline > 10
Temperature (°C)	Value > 38.3°C or change from baseline > 1.6°C

6.6.8 **Physical Examination Findings**

All physical examination abnormal findings will be listed per participant and visit.

6.7 **Pharmacokinetics**

The Pharmacokinetic (PK) population will be used for all listings. Evaluable PK population will be used for summary statistics and statistical analyses. Statistical analyses will be repeated excluding subjects with positive abatacept induced ADA responses. Analysis will include all valid analyte data for BMS-188667.

Subject serum concentration-time profiles will be listed and summarized by treatment and nominal collection time. Plot of individual serum concentration profiles over time will be provided. Overlay of individual serum concentration profiles over time will be provided by treatment. Plots of mean (+SD) serum concentration profiles versus time will be presented, for the first 24 hours and separately for the entire study duration on both linear and log-linear scale and both treatments will be superimposed on the same plot. Scatter plots of PK parameters for C_{max}, T-HALF, CLT, V_{ss}, AUC(0-28 day), AUC(0-T), and AUC(INF) will be produced for each treatment.

All individual PK parameters will be listed including any exclusions and reasons for exclusion. Summary statistics will be tabulated for each PK parameter by treatment. Geometric means and coefficients of variation will be presented for C_{max}, AUC(INF), AUC(0-T), AUC(0-28 day), CLT and V_{ss}. Medians and ranges will be presented for T_{max}. Means and standard deviations will be presented for other PK parameters (i.e., T-HALF). Decimal place specifications for summary statistics are described in Section 6.9.

To assess comparability of Treatment A (new drug substance process) to Treatment B (current drug substance process), an ANCOVA model will be fitted with treatment as a fixed effect and adjusted for baseline body weight. Point estimates and 90% CIs for treatment differences on the log scale for AUC(INF) and C_{max} will be exponentiated to express the results as ratios of geometric means and the corresponding 90% CIs on the original scale. Biocomparability of Treatment A to Treatment B will be concluded if the 90% CIs for the ratios of geometric means for abatacept C_{max} and AUC(INF) are contained within 80% to 125%.

[REDACTED]

In addition, the adjusted geometric mean ratios (GMRs) and corresponding 90% CIs for AUC(INF) and Cmax will be summarized in forest plots overall and by baseline weight class. These estimates will be obtained from a model with treatment and baseline body weight class as fixed effects.

[REDACTED]

A listing of subjects excluded from the Evaluable PK Population along with reasons for exclusion will be provided.

[REDACTED]

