10 STATISTICAL CONSIDERATIONS

10.1 Sample Size Determination

Biocomparability of Treatment A to Treatment B will be concluded if the 90% CIs for the ratios of geometric means for abatacept C_{max} and AUC(INF) are contained within 80% to 125%. Seventy participants per treatment group (Treatment A or Treatment B) will provide 88% power to conclude that Treatment A is biocomparable to Treatment B if Treatment A increases abatacept exposure by 10% compared to Treatment B; if Treatment A decreases abatacept exposure by 10%, 70 participants per treatment group will provide 83% power to conclude that Treatment A is biocomparable to Treatment B.

Participants who drop out will be replaced to ensure that there will be at least 65 evaluable participants per treatment group. Sixty-five participants per treatment group will provide 86% power to conclude that Treatment A is biocomparable to Treatment B if Treatment A increases abatacept exposure by 10% compared to Treatment B and 80% power if Treatment A decreases abatacept exposure by 10%.

These calculations assume that AUC(INF), and Cmax are log-normally distributed with between-participant standard deviation of 0.21 for Cmax and 0.27 for AUC(INF), [REDACTED]

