2.2 Treatment Assignment

Participants will be randomized on Day 1 in a 1:1 ratio to either Treatment A or Treatment B groups. The randomization will be stratified by weight categories: ≥ 60 to < 70 kg, ≥ 70 to < 80 kg, ≥ 80 to < 90 kg, and ≥ 90 to ≤ 100 kg according to a computer generated randomization scheme prepared by ICON.

Within each weight category, participants will be randomly assigned to abatacept drug product converted from drug substance by a new drug substance process (Treatment A) or abatacept drug product converted from drug substance by the current drug substance process (Treatment B).

In order to decrease variability, the goal of the treatment group assignment is to match each participant 1:1 by weight category to a participant with the opposite treatment assignment. A minimum of 10 participants per treatment per weight category are planned to be randomized.

Randomization numbers will be sequential within each weight category, starting with 1001, 2001, 3001, and 4001 for ≥ 60 to < 70 kg, ≥ 70 to < 80 kg, ≥ 80 to < 90 kg, and ≥ 90 to ≤ 100 kg weight categories, respectively. A copy of the randomization listing will be provided to the pharmacist prior to study initiation.

Enrolled participants, including those not dosed, will be assigned sequential participant numbers starting with 00001 (eg, 00001, 00002, 00003.... 00010). Sequential numbering may restart at 00001 for each participating site as the distinct patient identification number (PID) will ultimately be comprised of the site number and participant number, (eg, 0002-00001). Those enrolled participants meeting inclusion and exclusion criteria will be eligible to be randomized.

Randomization numbers will be assigned prior to dosing.

Participants will not be replaced if they are discontinued from the study secondary to an AE unless the AE can be determined to be unrelated to treatment. If a participant is replaced after dosing, the replacement participant will be identified from the same site and from the same weight category to the discontinued participant. The replacement participant will receive the same treatment as the participant that was discontinued but a new randomization number will be assigned to him or her. The new randomization number will be the original randomization number plus 4000. For example, Participant 1004 would be replaced by Participant 5004.

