7 CONTENT OF REPORTS

Statistical components for the clinical study report will be based on the content of this statistical analysis plan (SAP). Details of the tables, listings, and figures to be prepared for the final CSR will be included in a study-specific Data Presentation Plan (DPP).

- [REDACTED]
- [REDACTED] [REDACTED] [REDACTED] [REDACTED] [REDACTED] [REDACTED] [REDACTED] [REDACTED]
[REDACTED]
- [REDACTED]
[REDACTED]

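### The weight-class forest plot is specified with an additive model, so every class row will repeat the overall A/B ratio and its 90% CI

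*SAP*

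**What the plan says.** SAP section 2.2 makes weight category the stratification factor ("The randomization will be stratified by weight categories"), with four classes from 60 to 100 kg, 1:1 allocation, and this target for cell size: "A minimum of 10 participants per treatment per weight category are planned to be randomized".

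The primary comparison in SAP section 6.7 uses body weight as the covariate: "an ANCOVA model will be fitted with treatment as a fixed effect and adjusted for baseline body weight". The biocomparability conclusion rests on the 90% CIs for Cmax and AUC(INF).

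The same section then adds a supplementary display. Adjusted GMRs and 90% CIs for the two primary parameters "will be summarized in forest plots overall and by baseline weight class". The next sentence names the source of all these numbers: "These estimates will be obtained from a model with treatment and baseline body weight class as fixed effects". No readable text in the SAP or the protocol adds an interaction or a fit within each class. Protocol section 10.3.1 describes only the weight-adjusted ANCOVA and no forest plot.

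**The concern.** A by-class forest plot is meant to show whether the A/B ratio is similar in light and heavy participants. The named model assumes that it is. With treatment and class as main effects only, the figure would show five identical rows per parameter. A reader could take this for evidence of consistency across weight when the model has imposed it.

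The class intervals would mislead in the same way. Each would be the interval for a common ratio estimated from the whole study, printed on a row labelled as one weight class. This is the only visible planned display of the A/B ratio by class.

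**Working it through.** **Inputs.** Log-scale between-participant SDs are 0.21 for Cmax and 0.27 for AUC(INF) (protocol 10.1, SAP 4). There are 70 per arm, with a floor of 65 evaluable. There are four classes, with a planned minimum of 10 per arm in each (SAP 2.2). Intervals are two-sided 90%.

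**The plan's own figures.** Power is Φ[(distance from the true log ratio to the nearer margin)/SE − 1.645], with SE = SD·√(2/n). For AUC(INF) at n = 70, SE = 0.27 × √(2/70) = 0.0456.
- +10%: (ln 1.25 − ln 1.10)/0.0456 − 1.645 gives 87.6% (stated 88%).
- −10%: (ln 0.90 − ln 0.80)/0.0456 − 1.645 gives 82.5% (stated 83%).
- n = 65: 85.4% and 80.0% (stated 86% and 80%).

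The stated power is reproduced closely, so the SD, sample size and confidence level used below are those behind the plan.

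**Why the rows coincide.** Write the named model as log(y) = μ + τ·[A] + γ(class). In class k, the A-minus-B difference is (μ + τ + γk) − (μ + γk) = τ. The class term cancels, so each class row and the overall row are the same estimate of τ with the same standard error. This is algebra and needs no assumption about the data.

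**Illustration.** Log AUC(INF) was simulated with SD 0.27, 70 per arm, near-equal classes, and assumed true class ratios of 1.25, 1.10, 1.00 and 0.85.

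| Row | Additive model | With interaction |
|---|---|---|
| Overall | 1.058 (0.986-1.135) | not applicable |
| True 1.25 | 1.058 (0.986-1.135) | 1.221 (1.067-1.397) |
| True 1.10 | 1.058 (0.986-1.135) | 1.129 (0.986-1.291) |
| True 1.00 | 1.058 (0.986-1.135) | 1.049 (0.913-1.205) |
| True 0.85 | 1.058 (0.986-1.135) | 0.856 (0.745-0.984) |

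**Size of the precision gap.** The log half-width is t(0.95, df)·SD·√(2/m), with arms equal within class. For the additive model m = 70 and df = 140 − 5 = 135. For the interaction model m is the class size per arm and df = 140 − 8 = 132. If each class has at least 10 per arm, one class can hold at most 70 − 30 = 40; the average is 70/4 = 17.5.

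| | AUC(INF) half-width (CI at GMR 1) | Cmax half-width (CI at GMR 1) | Ratio to additive |
|---|---|---|---|
| Additive, every row | 0.076 (0.927-1.079) | 0.059 (0.943-1.061) | 1 |
| Interaction, 40 per arm | 0.100 (0.905-1.105) | 0.078 (0.925-1.081) | 1.3 |
| Interaction, 17.5 per arm | 0.151 (0.860-1.163) | 0.118 (0.889-1.125) | 2.0 |
| Interaction, 10 per arm | 0.200 (0.819-1.221) | 0.156 (0.856-1.168) | 2.65 |

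The ratios do not depend on the SD. At 65 evaluable per arm (df 125 and 122) they are 2.0 at the average of 16.25, 2.55 at 10 and 1.36 at 35. The last two assume that the minimum of 10 also holds among evaluable participants.

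**The case against.** The strongest reply is that the SAP sentence is shorthand. It lists the factors without saying that they are not crossed, and the promise of estimates by class implies something more than an additive fit. The missing term might also sit in the redacted blocks before and after the paragraph, or in the Data Presentation Plan to which SAP section 7 refers for figure details. None of this can be excluded. But the sentence is complete, and it covers the overall and class rows together. Separate fits do not match it either, since class would be constant within each fit. Section 7 also says that the report's statistical components follow the SAP, so the model belongs there.

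Three further points stand at least in part.
- The additive interval is a correct interval for a common ratio. It is too narrow only when read as class-specific, which is how a class row in this figure would be read.
- The figure is supplementary and has no decision rule. Identical rows would probably be noticed in draft output, and individual parameters and body weights are listed anyway. That limits the harm, but it leaves the model to be chosen after data are available in an open-label study.
- The minimum of 10 is a plan for randomized participants, not a guarantee among evaluable ones. If all five losses per arm fell in a class of 10, its ratio would be about √(65/5) = 3.6. If none fell in a class of 40, that class's ratio would be about √(65/40) = 1.27. The 65-per-arm figures are therefore not strict bounds.

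**Conclusion.** The concern holds. As written, the weight-class rows carry no class-specific information and show intervals that genuine class estimates would exceed by a factor of about 2 at the average class size. With 70 evaluable per arm and the planned minimum met, the factor runs from 1.3 to 2.65. The identity of the rows is exact. The absolute widths rest on the planning SDs, because the documents do not give the weight-adjusted residual SD, and on equal arms within class.

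The consequence is confined to this supplementary figure. The correction is worth making because weight class is the factor the design stratifies on. The reading is of the visible text; a redacted block that specifies class-level estimation would resolve it.

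**What to change.** Replace the model sentence in SAP section 6.7 with wording such as: *Class-specific GMRs and 90% CIs will be obtained from a model with treatment, baseline weight class and their interaction as fixed effects.* Separate fits per class are an acceptable alternative if stated.

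Also state which model gives the overall row. Either the additive model or the primary ANCOVA would serve; the latter keeps the plotted overall result identical to the primary one. Label the class rows as descriptive and not assessed against 80-125%, since at 10 per arm the expected AUC(INF) interval at a true ratio of 1 already spans 0.819-1.221.

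The cost is one sentence and one model term, plus the wider class intervals shown above. Separate fits lose a little more because each estimates its own variance: for AUC(INF), a half-width of 0.154 rather than 0.151 at 17.5 per arm (df 33), and 0.209 rather than 0.200 at 10 per arm (df 18). Sample size, data collection and the primary analysis do not change.

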6.8.1 Immunogenicity

On Day 1, the immunogenicity sample should be drawn at predose.

Participants who seroconvert and continue to have a high titer at study discharge that is considered to be significantly increased versus baseline will be asked to return for follow-up assessment(s) for anti-abatacept antibodies approximately every 4 months until their titers and/or sero-status are judged to be stable by the investigator.

Lack of immunogenicity is defined as the absence of a positive antibody response generated against abatacept. A participant is considered to have a positive abatacept-induced immunogenicity for “CTLA4 and possibly immunoglobulin (Ig)” and “Ig and/or Junction Region” if one of the following criteria are met:

1. A missing baseline immunogenicity measurement and a positive laboratory-reported immunogenicity response after baseline.

2. A negative laboratory-reported baseline immunogenicity response and a positive laboratory-reported immunogenicity response after baseline.
3. A positive laboratory-reported baseline immunogenicity response and a positive laboratory-reported immunogenicity response after baseline that has a titer value strictly greater than the baseline titer value.

This definition will be applied for each antibody-reactivity separately. All other electrochemiluminescence (ECL) immunogenicity measurements will be classified as negative.

The incidence of laboratory-reported positive responses and the corresponding titer values will be listed by participant and by study day. The frequency and percentage of positive, abatacept-induced immunogenicity response will be summarized by treatment.

Titer will be listed.

The number and percentage of subjects with a positive neutralizing antibody response will be summarized by treatment group and study day. The summary will include all subjects with a positive abatacept-induced immunogenicity response.

Neutralizing antibody data will be listed.

[REDACTED]

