9.8.2 Immunogenicity Assessments

Table 9.8.2-1 lists the sampling schedule to be followed for immunogenicity assessments. Blood samples for determination of antibodies to abatacept and time-matched PK samples will be collected on Days 1, 15, 29, 57, and 71. Participants who seroconvert and continue to have a high titer at study discharge that is considered to be significantly increased versus baseline will be asked to return for follow-up assessment(s) for anti-abatacept antibodies approximately every 4 months until their titers and/or sero-status are judged to be stable by the investigator.

Table 9.8.2-1: Immunogenicity Sample Schedule

Study Day of Sample Collection	Event	Time (Relative To Start of Infusion of Abatacept Hour: Min)	Blood Sample for Immunogenicity
1	predose	00:00	X
15		336:00	X
29		672:00	X
57		1344:00	X
71		1680:00	X

A validated, sensitive, electrochemiluminescence assay (ECL) method will be used to detect anti-abatacept-antibodies with specificities to “CTLA4 and possibly Ig” and “Ig and/or Junction Region”.³⁴

Samples that are confirmed positive with specificity to “CTLA4 and possibly Ig” antibodies with the ECL immunogenicity assay will be further analyzed with a validated, in vitro, cell-based bioassay to determine whether the anti-abatacept-antibodies have neutralizing activity.

Record the date and time of sample collection so that compliance with the sampling schedule can be confirmed. Detailed instructions for the immunogenicity blood collection, labeling, processing, storage, and shipping will be provided to the site in the procedure manual.

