10.3.3 Other Analyses

10.3.3.1 Immunogenicity

Endpoint	Statistical Analysis Methods

anti-abatacept antibodies antibodies specific for ‘CTLA4 and possibly Ig’ and ‘Ig and/or Junction Region’
	
The incidence of laboratory-reported positive responses and the corresponding titer values will be listed by participant and by study day.
 
The frequency and percentage of positive abatacept-induced immunogenicity response will be summarized by treatment.

Lack of immunogenicity is defined as the absence of a positive antibody response generated against abatacept.

A participant is considered to have a positive abatacept-induced immunogenicity for ‘CTLA4 and possibly Ig’ or ‘Ig and/or Junction Region’ if 1 of the following criteria are met:

A missing baseline immunogenicity measurement and a positive laboratory-reported immunogenicity response after baseline.

- A negative laboratory-reported baseline immunogenicity response and a positive laboratory-reported immunogenicity response after baseline.
- A positive laboratory-reported baseline immunogenicity response and a positive laboratory-reported immunogenicity response after baseline that has a titer value strictly greater than the baseline titer value.

This definition will be applied for each antibody-reactivity separately. All other ECL immunogenicity measurements will be classified as negative.

[REDACTED]

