6.1 General Methods

All data recorded on case report forms will be listed by participant. Descriptive summaries will be presented for continuous variables using number of subjects (N), mean, SD, median, minimum, and maximum. Geometric mean and coefficient of variation (%CV) will also be presented for PK parameters as applicable. Descriptive summaries for categorical variables will utilize counts and percentages.

Where appropriate, baseline is defined as the last nonmissing result with a collection date-time less than the date-time of the first dose of study treatment.

Adverse events and medical history will be coded according to the most recent Medical Dictionary for Regulatory Activities (MedDRA) version. Previous and concomitant medications will be coded using the World Health Organization (WHO) Drug Dictionary.

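### For participants already antibody-positive at baseline, any one of four later titers above a single baseline titer counts as abatacept-induced, with no minimum rise, so assay noise alone can trigger the label

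*SAP*

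**What the plan says.** Both documents give three routes to a positive abatacept-induced response: baseline missing and later positive, baseline negative and later positive, or baseline positive and then a "positive laboratory-reported immunogenicity response after baseline that has a titer value strictly greater than the baseline titer value" (SAP 6.8.1). Protocol 10.3.3.1 has the same third route: the later sample "has a titer value strictly greater than the baseline titer value".

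The sampling plan is in Protocol 9.8.2: "Blood samples for determination of antibodies to abatacept and time-matched PK samples will be collected on Days 1, 15, 29, 57, and 71". Day 1 is predose, so four scheduled samples follow it. SAP 6.1 fixes a single comparator: "baseline is defined as the last nonmissing result with a collection date-time less than the date-time of the first dose of study treatment". On the two specificities, SAP 6.8.1 adds: "This definition will be applied for each antibody-reactivity separately".

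The label is used in three places:
- the frequency and percentage by treatment (SAP 6.8.1), which serve the secondary immunogenicity objective;
- the neutralizing-antibody summary, which takes in everyone with the label (SAP 6.8.1);
- the PK repeat in SAP 6.7: "Statistical analyses will be repeated excluding subjects with positive abatacept induced ADA responses".

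The visible text gives no minimum rise, confirmation sample, replicate rule, dilution factor, titer precision or expected share of baseline-positive participants.

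**The concern.** For a baseline-positive participant the rule amounts to asking whether the largest of four later titers exceeds one earlier titer. If the antibody is pre-existing and stable, all five values differ only by measurement error, and the largest of four has a built-in advantage over a single value. The label then attributes noise to the drug.

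Three things follow. The incidence attributed to abatacept is inflated in both arms. A chance imbalance in baseline positivity can look like a difference between the two processes. Some participants without an induced response are dropped from the antibody-excluded PK repeat or counted in the neutralizing-antibody summary. The planned percentage does not separate these cases from participants who turned from negative to positive.

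**Working it through.** The plan states no false-label rate for this rule, so there is no figure to reproduce.

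**Inputs from the documents.** One baseline value (SAP 6.1); k = 4 later samples (Protocol 9.8.2); strict inequality (SAP 6.8.1, Protocol 10.3.3.1); about 140 participants, 70 per arm (Protocol 5.2).

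**Assumptions.** No true titer change, all later samples remain positive, independent noise of equal size, no drug interference. Titer SD and dilution step are not given, so they are varied.

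**Continuous titers.** The baseline and the k later values are exchangeable, so P(largest later value > baseline) = k/(k+1) = 4/5 = 80%, whatever the noise SD. One later sample would give 1/2 = 50%.

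**Two-fold dilution titers.** Each true log2 titer sits uniformly within a dilution step, normal noise is added, and the value is rounded down to the step. Simulation with at least 400,000 draws per row gives:

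| Noise SD (steps) | Any of 4 above baseline | Any of 4 at least 2 steps above |
|---|---|---|
| 0.1 | 12% | <0.1% |
| 0.25 | 29% | 0.1% |
| 0.3 | 34% | 0.5% |
| 0.5 | 51% | 7% |
| 0.75 | 61% | 22% |
| 1.0 | 66% | 35% |

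These rates are per reactivity. Someone positive on both has two chances: at SD 0.5 and with independent noise, 1 − (1 − 0.505)² = 0.755.

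**Departures that lower the rate.**
- If circulating drug lowered all four later titers by one step, the strict rule would need noise of two steps to fire. The right-hand column then applies: 0.1%, 7%, 22% and 35% at SD 0.25, 0.5, 0.75 and 1.0.
- If the true level is near the positivity cut point, selecting on a positive baseline favours a high baseline draw. With continuous titers the rate falls from 80% to 61% when the true level is at the cut point, and to 27% when it is 1 SD below.

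**Number of people.** Baseline positivity is not stated. Assuming 5%: 0.05 × 140 = 7 people; 7 × 0.29 = 2.0 and 7 × 0.80 = 5.6, so about 2 to 6 false labels. One extra baseline-positive participant in an arm of 70 adds between 0.29/70 = 0.4 and 0.80/70 = 1.1 percentage points to that arm.

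**Effect on the A-versus-B difference.** Let b be the baseline-positive share, f the false-label rate, and pA and pB the true induction rates among baseline-positive participants. The observed rate in that stratum is p + (1 − p)f, so its difference becomes (pA − pB)(1 − f). The overall loss is b × f × (pA − pB). Even at b = 10% and f = 80% this is 0.08 × (pA − pB).

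**Sensitivity given up by a two-step threshold.** For a sustained true two-fold rise, detection falls from 97% to 29% at SD 0.25 and from 93% to 51% at SD 0.5.

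**The case against.** The strongest reply is that this is a deliberately sensitive, pre-specified definition in a descriptive summary with no formal test. Positive responses and titers are listed by participant and study day, so baseline-positive cases can be found. The PK analysis without antibody-positive participants is only a repeat. Neutralizing testing is triggered by a confirmed positive for the CTLA4 specificity, not by this label (Protocol 9.8.2). Table detail is left to a Data Presentation Plan that is not among the documents. All of this stands, and it limits the consequence. It does not change what the headline percentage counts.

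The size is also open to challenge. A reader might infer that noise triggers the label in half to 80% of baseline-positive participants. The documents do not support that as an unconditional rate. They say "A validated, sensitive, electrochemiluminescence assay (ECL) method will be used to detect" the antibodies, but give no titer scale or precision. 80% is a ceiling under exchangeable noise, about half needs an SD of roughly 0.5 step, and precise titers, drug interference or levels near the cut point give much less.

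A reader might also see a contradiction with the follow-up rule in Protocol 9.8.2, for seroconverters who "continue to have a high titer at study discharge that is considered to be significantly increased versus baseline". There is none: that rule decides who returns after discharge, and its standard is undefined. It shows only that the plan elsewhere treats a marked rise as different from any rise.

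**Conclusion.** The point holds as a cheap improvement. As written, the third criterion can assign assay noise to the drug in participants with a stable pre-existing antibody. The rate per reactivity is at most 80% under exchangeable noise. With two-fold titers it is about 12% to 66% over an assumed SD of 0.1 to 1.0 step, and lower where drug suppresses titers or the level is near the cut point. How many people this touches cannot be settled from the documents; if baseline positivity is near zero, the effect is negligible.

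Two stronger readings fail. The rule does not materially pull the absolute difference between treatments towards zero: it is the same in both arms, and the loss is a small fraction of the difference among baseline-positive participants. What remains is inflated incidence in both arms and exposure to chance imbalance in baseline positivity. Nor does it affect biocomparability, because the primary Cmax and AUC(INF) analysis does not use the label.

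**What to change.** In SAP 6.8.1 and Protocol 10.3.3.1:

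1. Split the by-treatment table: participants negative or missing at baseline who become positive in one row, baseline-positive participants with a titer rise in another.
2. For the second row, require a rise that exceeds the titer assay's validated reproducibility, and state the dilution factor and precision it rests on. Four-fold on a two-fold series is only an example: it leaves about 7% false labels at SD 0.5 step but 35% at SD 1.0, so the threshold should come from the validation data.
3. Use the revised label for the antibody-excluded PK repeat (SAP 6.7) and the neutralizing-antibody summary.
4. Keep the strict definition as a supplementary row.

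The cost is one changed criterion and added table rows, using titers already collected; the validation figures must come from the assay laboratory. The statistical price is the loss of sensitivity to small true rises shown in the working. Those cases remain visible in the supplementary row and the titer listing. If the threshold is left alone, the first step by itself still removes most of the ambiguity.
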